3.6.2. PLACEBO

The placebo will be sterile VM202 vehicle. Components of VM202 vehicle are provided in Table 4. VM202 excipients are supplied in a sterile glass vial in liquid form. Each vial is only to be used for one subject. Visually, VM202 vehicle is indistinguishable from reconstituted VM202.

Table 4. Components of VM202 Vehicle

COMPONENT	Function	Composition	

3.6.3. PRODUCT ACCOUNTABILITY

In accordance with federal regulations (21CFR 312.62), all Investigators or his/her designee are required to keep accurate records showing final disposition of all investigational drugs.

Investigational drugs are to be used only in accordance with this protocol and under supervision of the Study Pharmacist or a duly designated person. The Study Pharmacist or his/her designee will maintain an accurate record of the receipt of the VM202 and placebo as shipped by the Sponsor/Designee, including the date received. In addition, an accurate study drug disposition record will be kept, specifying the date and amount dispensed to each subject. This inventory record must be available for inspection at any time by the unblinded Pharmacy Monitor. Copies of this record will be provided to the Sponsor by the Study Pharmacist at the conclusion of the study.

After the study is completed, the Study Pharmacist must account for all study drug used, unused and partially used. Unused study medication from the study site will be returned to the Sponsor/Designee as directed in writing by the Sponsor or designee for gross reconciliation.

3.6.4. Dose and Administration

VM202 is supplied in a sterile glass vial containing and mg of study product. Before administration, it will be reconstituted with 5 mL of water for injection (WFI) by the study pharmacist for a final VM202 concentration of mg/mL. Each reconstituted vial is only to be used for one subject. The VM202 arm will receive only VM202 injections. The placebo group will receive only VM202 vehicle injections. All subjects will receive 16 injections per calf per visit. A complete description of test article administration can be found in Appendix 7.

3.7. PRIOR AND CONCOMITANT MEDICATION

All concomitant medications (taken within 60 days of the first injection) will be recorded at each study visit. For each medication taken, the following information will be collected:

- Medication trade name;
- Indication for which the medication was given;
- Dose/strength, route, and frequency of administration;
- Date started and date stopped (or continuation at study exit).

EXAMINATIONS AND EVALUATIONS 4.

4.1. **EVALUATIONS CONDUCTED AT BASELINE ONLY**

MEDICAL HISTORY 4.1.1.

A complete medical history will be obtained at Baseline. All positive and negative findings will be carefully documented on the study worksheets. Any new finding discovered during the Screening/Baseline evaluation and prior to the first study drug administration (Day 0) will be considered to be part of the medical history and will not be recorded as an adverse event.

The Investigator will perform an especially detailed assessment of past diabetes history to include all events and interventions prior to study enrollment. Other potential causes of peripheral neuropathy will be excluded (e.g., alcohol consumption, renal failure, liver disease, hypothyroidism, collagen vascular diseases, vasculitis, osteoarthritis of the ankle or foot, gout, bursitis, fasciitis, and B-12 or folate deficiency).

4.1.2. PHYSICAL EXAM

A physical exam will be performed at Screening. The exam will include the following: head, eyes, ears, nose, and throat (HEENT), heart, lungs, abdomen, extremities, lymph nodes, musculoskeletal, neurological, and gastrointestinal systems. Any abnormalities should be categorized as clinically significant (CS) or not clinically significant (NCS), and the abnormalities should be recorded in the subject's study worksheets. Actual height will be measured.

CANCER SCREENING 4.1.3.

All subjects participating in this trial must undergo routine cancer screening. The history and diagnosis of potential or apparent malignant and non-malignant diseases and neoplasms will be assessed through several diagnostic tests and procedures. Some diagnostic tests and procedures performed prior to study consent and documented in the subject's medical history may be acceptable where noted. Routine cancer screening includes the following:

- For subjects ≥ 50 years old, fecal occult blood test. A positive fecal occult blood test (current or reported within the past 12 month) requires follow-up testing which is beyond the scope of this study. If follow-up testing rules out cancer, the subject will be able to participate in the study if the subject is still interested. For subjects with medical history and/or family history of colon cancer in any first degree relative, must have documentation of a negative colonoscopy performed within past 12 months.
- Chest X-ray or chest CT scan within 3 months prior to study entry†: (if the subject is currently using tobacco or has a previous history [within 15 years] of tobacco use, a CT scan will be performed instead of X-ray).
- Mammogram within 1 year prior to study entry (females ≥ 40 years only)
- Papanicolaou (Pap) smear within 1 year prior to study entry \dagger (females ≥ 21 years only except for women who had a complete hysterectomy [removal of uterus and cervix] and females ≥ 70 years with 3 normal pap smears and no abnormal pap smear during the last 10 years).

VIRAL SCREENING

The local laboratory will be responsible for Screening viral testing and assays to include: HIV-1, HIV-2, HTLV, and HBV and HCV as determined by Hepatitis B core antibody (IgG and IgM; HBcAb), antibody to Hepatitis B antigen (HBsAb), Hepatitis B surface antigen (HBsAg) and Hepatitis C antibodies (Anti-HCV).

4.1.5. 12-LEAD EKG

A 12 lead electrocardiogram (EKG) will be conducted at Screening. The EKG recording will be printed out, and a copy will be placed with subject records. Any (clinically significant) abnormalities will be reported.

4.1.6. BRIEF PERIPHERAL NEUROPATHY SCREENING (BPNS)

Symptoms of BPNS will be assessed at initial screening in order to evaluate the bilateral extent of DPN (see Appendix 11).

4.1.7. PREGNANCY TEST (WOMEN OF CHILDBEARING POTENTIAL ONLY)

For women of childbearing potential, a urine beta human chorionic gonadotropin (β-HCG) test will be performed at Screening. Results of the test must be negative and effective contraception documented. Acceptable methods of contraception include:

- Barrier type devices (e.g., female condom, diaphragm and contraceptive sponge) used only in combination with a spermicide;
- Intrauterine device;
- Oral contraceptive agents;
- Depo-provera (medroxyprogesterone acetate);
- Levonorgestrel implants;

Protocol VMDN-003/H CONFIDENTIAL Helixmith Co., Ltd

[†] Study entry is defined as the date of signing informed consent.

Abstention, the rhythm method or contraception by a partner are not considered acceptable methods of contraception.

EVALUATIONS CONDUCTED THROUGHOUT THE STUDY 4.2.

4.2.1. RETINAL FUNDOSCOPY

Proliferative retinopathy, defined as the presence of new proliferating blood vessels (neovascularization) arising from the retina or optic disc and growing on the retinal surface or into the vitreous cavity, will be assessed by retinal fundoscopy at Screening for eligibility and repeated at Day 180 and Day 270. Retinal fundoscopy must be performed by an ophthalmologist within 3 months of Screening.

In cases where fundoscopy alone is deemed insufficient to determine eligibility, fluorescein angiography may be conducted at Screening.

4.2.2. **CONCOMITANT MEDICATIONS**

Concomitant medications will be recorded at each visit using the trade name or generic name as described in Section 3.7.

4.2.3. VITAL SIGNS

Vital signs consisting of blood pressure (while subject is sitting), temperature, weight, heart rate, and respiratory rate will be measured and recorded at Screening and at every visit through the 9-month follow-up.

4.2.4. SERUM CHEMISTRY, HEMATOLOGY AND HBA1C

Evaluation of serum chemistry and hematology will be conducted at Screening, Day 0, Day 90, Day 180 (6 months) and Day 270 (9 months). Evaluations will be conducted by a local laboratory at each site.

Serum chemistry evaluations will include: calcium, glucose, sodium, potassium, chloride, bicarbonate, blood urea nitrogen (BUN), creatinine, alanine aminotransferase (ALT), aspartate aminotransferase (AST), total bilirubin, alkaline phosphatase, albumin, and total protein.

Hematology evaluations will include: complete blood count (CBC): red blood cells (RBC); hemoglobin (Hgb), hematocrit (HCT), platelets and white blood cells (WBC) with differential. Abnormal readings do not necessarily constitute an adverse event; the results need to be reviewed in the context of the subject's health.

[figure not shown]
HbA1c will be determined at Screening, Day 0, Day 90, Day 180 (6 months) and Day 270 (9 months) at a local laboratory at each site. Laboratory testing by visit is provided in Appendix 1.

4.2.5. SERUM HGF

HGF serum levels will be determined immediately pre-treatment on Day 0, immediately pre-treatment on Day 14, on Day 21, Day 60, immediately pre-treatment on Day 90, immediately pre-treatment on Day 104, Day 111, Day 150, Day 180 and Day 270.

A minimum 6 cc blood draw will be taken at each time point. Allow blood to clot for 30-60 minutes at room temperature then centrifuge for 10 minutes at 1000 x g. Divide the isolated serum into six (6) equal aliquots of ~ 0.3 mL each. (0.5mL plastic storage tubes provided). Samples should be labeled with study number, subject ID, draw date, and visit interval (i.e., Day 0, 14, 21, 60, 90, 104, 111, 150, 180 or 270). Samples will be maintained in a cooler containing dry ice and then placed in a $\leq -65^{\circ}$ C freezer until shipped for analysis.

Serum HGF samples will be batched with VM202 samples and shipped bimonthly (i.e., odd months: January, March, May, July, September, November) in a special container with temperature tracking recorder to for analysis. Please see the

Note, will provide collection tubes, plastic vials, labels, shipment materials including temperature tracking devices to each participating site for use during the study.

4.2.6. COPIES OF VM202 IN WHOLE BLOOD

The number of copies of VM202 in whole blood will be determined by PCR at Day 0 (pre-injection, and 2 hours [± 1 hour] post injection), at Day 14 (pre-injection, and 2 hours [± 1 hour] post injection), Day 21, Day 60, at Day 90 (pre-injection, and 2 hours [± 1 hour] post injection), at Day 104 (pre-injection, and 2 hours [± 1 hour] post injection), Day 111, Day 150, Day 180 and Day 270.

Six (6) cc of whole blood will be collected in EDTA-coated tubes, inverted >5 times and transferred to plastic sterile and or RNase and DNase free vials of ~0.6 − 1 cc aliquots each for a total of 5 aliquots per time point. These will be maintained in a ≤ -65°C freezer until shipped for analysis. Samples should be labeled with study number, subject ID, draw date and time, and visit interval (i.e., Day 0 pre, Day 0 post, Day 14 pre, Day 14 post, Day 21, Day 60, Day 90 pre, Day 90 post, Day 104 pre, Day 104 post, Day 111, Day 150, Day 180 or Day 270).

VM202 samples will be batched with serum HGF samples and shipped bimonthly (i.e., odd months: January, March, May, July, September, November) in a special

container with temperature tracking recorder to for analysis. Please see the for detailed instructions.

Note, will provide collection tubes, plastic vials, labels, shipment materials including temperature tracking devices to each participating site for use during the study.

4.2.7. VISUAL ANALOG SCALE (VAS) SCORE

Pain will be recorded during site visits at Screening, Day 0 before the treatment (injection), on Day 90 before treatment (injection), at Days 180 and 270 using the visual analog scale (VAS). The VAS scoring instrument is a 100mm line, oriented horizontally, with the left end indicating "no pain" and the right end representing "very severe pain". The subject is asked to mark a place on the line corresponding to the current pain intensity. The distance along the scale is then converted into a numeric reading by measuring the distance of the subject's mark in millimeters from the beginning of the scale (the 0 mark). The VAS is illustrated in Appendix 9. Upon completion of the VAS, the study coordinator will check the VAS for completeness. Note, the subject will be required to initial and date the VAS.

4.2.8. DAILY PAIN AND SLEEP INTERFERENCE DIARY

Subjects will be asked to keep a Daily Pain and Sleep Interference Diary (see Appendix 10). Subjects will be asked to rate their 24-hour average daily pain intensity score using an 11-point numerical rating scale from 0 (no pain) to 10 (worst possible pain). The effect of pain on the subject's ability to sleep will be assessed using the sleep interference score. Like the pain intensity score, the sleep interference score is an 11-point numerical rating scale from 0 (pain did not interfere with sleep) to 10 (pain completely interfered; subject was not able to sleep due to pain).

The diary will be completed at Screening following wash-out of prohibited medications (if applicable), and within 14 days prior to the Day 90, Day 180 (6 months) and Day 270 (9 months) visits. To increase compliance, the Diary will be FedExed to the subject 2 weeks prior to the scheduled visit. The FedEx shipping bill will become part of the subject's source documents. Ten days prior to the scheduled visit, the study coordinator will call the subject to remind the subject of their upcoming visit at Day 90, Day 180 (6 months) or Day 270 (9 months), and the requirement to complete the diary starting within 14 days of the visit. The phone call will be documented on the source document worksheets. One day prior to the visit, the study coordinator at each site will call the subjects to confirm their upcoming visit and to remind the subject to bring the completed Diary. If the subject

arrives at the clinic without the completed diary, the visit will be rescheduled as soon as possible.

Optionally at the Day 90, Day 180 (Month 6) and Day 270 (Months 9) visits only (not at Screening): if the subject states that the Diary was completed and it is a hardship for the subject to reschedule the visit (e.g., distance or transportation issues), the site may provide a completed FedEx shipping bill to the subject so the subject can send the completed Diary to the site using FedEx.

Upon completion of the Diary, the study coordinator will check the Diary for completeness. Any omissions or ambiguous answers will be clarified by the subject prior to leaving the clinic. Note, the subject will be required to initial each page of the diary.

4.2.9. MICHIGAN NEUROPATHY SCREENING INSTRUMENT

The Michigan Neuropathy Screening Instrument (MNSI) will be conducted at Screening in order to confirm the diagnosis of diabetic peripheral neuropathy and at Day 180 (6 months) and Day 270 (9 months) to track disease progression. The MNSI is comprised of a subject questionnaire (15 questions) and of a physical evaluation which includes a foot inspection, vibration sensation testing, muscle stretch reflexes, and monofilament testing. The MNSI forms and instructions can be found in Appendix 5. Upon completion of the MNSI questionnaire, the study coordinator will check the questionnaire for completeness. Any omissions or ambiguous answers will be clarified by the subject prior to leaving the clinic. Note, the subject will be required to initial and date the MNSI questionnaire.

4.2.10. SEMMES WEINSTEIN MONOFILAMENT TEST

The Semmes-Weinstein monofilament test will be conducted at Day 0, 90 Days, Day 180 (6 months) and Day 270 (9 months). Testing will be performed on the plantar aspect of great toe, first, third and fifth metatarsal heads of each foot. The Semmes Weinstein monofilament test instructions can be found in Appendix 6.

4.2.11. BRIEF PAIN INVENTORY FOR SUBJECTS WITH DIABETIC PERIPHERAL NEUROPATHY (BPI-DPN)

The brief pain inventory (BPI-DPN) ^{55,56} will be self-administered during site visits on Day 0 before the treatment (injection), on Day 90 before the treatment (injection), and at 180 and 270 days. The Questionnaire includes numeric rating scale that assesses the severity of pain, its impact on daily functioning, and other aspects of pain (e.g. location of pain, relief from medications). The questionnaire was modified to distinguish between pain due to DPN and pain due to other causes. Upon completion of the questionnaire, the study coordinator will check the questionnaire for completeness. Any omissions or ambiguous answers will be clarified by the subject prior to leaving the clinic. The full Questionnaire can be found in Appendix 8. Note, the subject will be required to initial and date the BPI-DPN.

4.2.12. PATIENT'S GLOBAL IMPRESSION OF CHANGE (PGIC)

The patient's global impression of change after treatment will be measured using the Patient's Global Impression of Change (PGIC) questionnaire.⁶⁵ This questionnaire measures a patient's perception of how treatment has affected their level of activity, symptoms, emotions, and overall quality of life. Each descriptor is ranked on an intensity scale of 1 = Very Much Improved; 2 = Much Improved; 3 = Minimally Improved; 4 = No Change; 5 = Minimally Worse; 6 = Much Worse 7 = Very Much Worse. This test will be self-administered during study visits on Day 90, Day 180 and Day 270.

Upon completion of the questionnaire, the study coordinator will check the questionnaire for completeness. Any omissions or ambiguous answers will be clarified by the subject prior to leaving the clinic. The PGIC can be found in Appendix 12. Note, the subject will be required to initial and date the PGIC.

4.2.13. Nerve Conduction Testing

Nerve conduction testing will be conducted pre-treatment on Day 0, Day 180 and Day 270 at select sites. Unilateral testing will be performed on the sural sensory nerve and peroneal motor nerve of the left leg. The nerve conduction testing instructions can be found in Appendix 13.

4.2.14. INJECTION SITE REACTION ASSESSMENT

Local injection sites reactions will be assessed on Day 0 post injection, Day 14 pre and post injection, Day 21, Day 60, Day 90 pre and post injection, Day 104 pre and post injection, and at Day 111 and Day 150 Injection site reactions will be completed using the Injection Site Adverse Event form. The location (calf area) and temporal relationship to the most recent injections will determine whether the event is an injection site reaction or adverse event.

Table 5. Injection Reaction Assessment

ADVERSE EVENT	GRADE 1	GRADE 2	GRADE 3	GRADE 4	GRADE 5
Injection site reaction	Pain, itching, erythema	Pain or swelling, with inflammation or phlebitis	Ulceration or necrosis that is severe; operative intervention indicated		
Ulceration		Superficial ulceration < 2 cm size; local wound care; medical intervention indicated	Ulceration ≥2 cm size; operative debridement, primary closure or other invasive intervention indicated (e.g. hyperbaric oxygen)	Life-threatening consequences; major invasive intervention indicated (e.g., complete resection, tissue reconstruction, flap, or grafting	Death
Allergic reaction / hypersensitivity	Transient flushing or rash; drug	Rash; flushing; urticaria; dyspnea; drug	Symptomatic bronchospasm, with or without urticaria;	Anaphylaxis	Death

ADVERSE EVENT	GRADE 1	GRADE 2	GRADE 3	GRADE 4	GRADE 5
	fever < 38°C (<100.4°F)	fever ≥38°C (≥100.4°F)	parenteral medications(s) indicated; allergy-related edema/ angioedema; hypotension		

5. EVALUATION OF ADVERSE EVENTS

5.1. **DEFINITIONS**

An Adverse Event (AE) is the development of an untoward medical occurrence or the deterioration of a pre-existing medical condition following or during exposure to an investigational product, whether or not considered causally related to the product.

An untoward medical condition can be symptoms (e.g., nausea, chest pain), signs (e.g., tachycardia, enlarged liver) or clinically significant abnormal results of an investigation (e.g., laboratory findings, electrocardiogram).

Conditions or diseases that are chronic but stable should not be recorded as an AE. Changes in a chronic condition or disease that are consistent with natural disease progression are NOT considered AEs and also should not be recorded on AE worksheets. These medical conditions should be adequately documented on the appropriate page of the study worksheet (relevant medical history and/or physical examination). However, medical conditions present at enrollment that worsens in intensity or frequency in a manner inconsistent with the natural course of the disease during the treatment or post-treatment periods should be reported and recorded as AEs.

An **adverse reaction** means any adverse event caused by a drug. Adverse reactions are a subset of all suspected adverse reactions for which there is reason to conclude that the drug caused the event.

Suspected adverse reaction means any adverse event for which there is a reasonable possibility that the drug caused the adverse event. For the purposes of IND safety reporting, 'reasonable possibility' means there is evidence to suggest a causal relationship between the drug and the adverse event. A suspected adverse reaction implies a lesser degree of certainty about causality than adverse reaction, which means any adverse event caused by a drug.

A serious adverse event (SAE) is any untoward medical occurrence which:

- Results in death:
- Is life-threatening;

- Requires inpatient hospitalization (admission to hospital with a stay > 24 hours) or prolongation of hospitalization which is not specifically required by the protocol or is elective;
- Results in permanent impairment of a body function or permanent damage to a body structure; or
- Requires medical or surgical intervention to preclude permanent impairment of a body function or permanent damage to a body structure.

Additionally, important medical events that may not result in death, be life-threatening or require hospitalization may be considered SAEs when they jeopardize the subject or require medical or surgical intervention to prevent one of the serious outcomes listed above. Examples of such medical events include: allergic bronchospasm requiring intensive treatment in an emergency room or at home, blood dyscrasias or convulsions that do not result in inpatient hospitalization or the development of drug dependency or drug abuse. Medical and scientific judgment must be exercised when classifying events as serious.

Life-threatening means that the subject is, in the view of the investigator, at immediate risk of death from the AE as it occurred. It does not include an AE which, had it occurred in a more serious form, might have caused death.

Persistent or significant disability/incapacity means that the event resulted in permanent or significant and substantial disruption of the subjects' ability to carry out normal life functions.

An **unexpected AE** is an AE, the nature or severity of which is not consistent with the applicable product information (e.g., Investigator Brochure for an unapproved product). Expected means that the event has been previously observed with the test article and is identified and/or described in the applicable product information. It does not mean that the event is expected with the underlying disease(s) or concomitant medications. It is expected that certain disease states will have reoccurring adverse events some of which may be considered expected over time.

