5.4. REPORTING / RECORDING OF SAES

5.4.1. INVESTIGATOR'S RESPONSIBILITY

SAEs will be recorded following the first study drug administration through the 9-month follow-up visit. Any serious adverse event or unexpected adverse event that occurs during this investigation, whether or not related to the study medication, must be reported as soon as possible but no later than 3 working days after the investigator first learns of the event to the Sponsor and the designated CRO by completing the SAE form and the AE information in the EDC and selecting appropriate criteria that classifies the AE as serious and/or unexpected. In order to have the Investigator's signature on file, the signed SAE form needs to be uploaded to the EDC at the time of initial data entry.

Each SAE must be followed with appropriate medical management until resolved or assessed as chronic or stable regardless of whether or not, in the opinion of the Investigator, the event is thought to be related to the study medication.

The Investigator will be required to provide complete information (including the Investigator's opinion of the relationship of the SAE to the study medication) concerning each SAE to the CRO and Sponsor within 5 working days of first learning of the event. This information must be recorded in the subject's medical record and then entered into the EDC. Copies of related source documentation such as results/reports, hospitalization records, and other relevant information must be obtained if possible.

In the event of an SAE leading to hospitalization, every effort will be made by the investigational site to obtain medical records, including a hospital discharge summary. In the event of a fatal AE, documentation of any available postmortem findings, including autopsy, will be provided to the Sponsor or their designee. In any event, the Investigator will provide a narrative summary of circumstances, events related to the death, and cause of death, if known.

The Investigator must comply with the applicable local regulatory requirements related to the reporting of SAEs to regulatory authorities and the Institutional Review Board (IRB), and Institutional Biosafety Committee (IBC) if applicable. Upon receipt from the Sponsor of an initial or follow-up IND Safety Report or other

safety information, the Investigator must promptly notify his or her IRB, and IBC (if applicable).

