Adverse Event	An adverse event (AE) is the development of an untoward medical occurrence or the deterioration of a pre-existing medical condition following or during exposure to an investigational product, whether or not it is considered causally related to the product. Changes in a chronic condition or disease that are consistent with natural disease progression are NOT considered AEs.
Baseline	The last non-missing value prior to first dose of study drug.
Serious AE	Any untoward medical occurrence which results in death; is a life-threatening experience; requires hospitalization (admission to hospital with a stay > 24 hours) or prolongation of an existing hospitalization which is not specifically required by the protocol or is elective; results in permanent impairment of a body function or permanent damage to a body structure; or requires medical or surgical intervention to preclude permanent impairment of a body function or permanent damage to a body structure.
Treatment Emergent Adverse Events	Adverse events that occur after dosing and pre-existing medical conditions that worsen following exposure to an investigational product.

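### The SAE criteria in Protocol 5.1 and the SAP omit the disability/incapacity criterion that the protocol itself defines, so significant but non-permanent disability is serious only at the investigator's discretion

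*Protocol*

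**What the plan says.** Protocol 5.1 (Definitions) gives five criteria for a serious adverse event:

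- death;
- "Is life-threatening";
- "Requires inpatient hospitalization (admission to hospital with a stay > 24 hours) or prolongation of hospitalization", with exceptions for elective or protocol-required stays;
- "Results in permanent impairment of a body function or permanent damage to a body structure";
- "Requires medical or surgical intervention to preclude permanent impairment of a body function or permanent damage to a body structure".

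The same section then adds a clause outside the list: "important medical events that may not result in death, be life-threatening or require hospitalization may be considered SAEs when they jeopardize the subject", or when they need intervention to prevent one of the listed outcomes. It asks for medical and scientific judgment in classifying events.

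Among the explanatory definitions that follow is this one: "Persistent or significant disability/incapacity means that the event resulted in permanent or significant and substantial disruption" of the subject's ability to carry on ordinary life.

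The SAP's Definitions table (Serious AE) repeats the five criteria, including "results in permanent impairment of a body function or permanent damage to a body structure". It contains neither the disability/incapacity criterion nor the important-medical-event clause.

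**The concern.** The definition of disability/incapacity is wider than anything in the list. Both function-related criteria turn on permanence, whereas the definition also covers disruption that is significant and substantial without being permanent. Yet the defined term is not a criterion, so the definition has nothing to act on. It reads as a criterion dropped from the list.

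The type of harm matters in this trial. Each subject receives 16 injections in each of two calves, so 16 × 2 = 32 per visit, and 32 × 4 visits = 128 in all. The population already has painful neuropathy in both legs. A spell of lost walking ability that resolves without a hospital stay is a relevant kind of event. At stake is whether such an event is classified as serious in the same way at every site, and what depends on that classification in expedited reporting and in the planned safety tables.

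**Working it through.** No arithmetic settles this point. The check sets the definitions side by side.

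**1. A test event.** Take a loss of walking ability that lasts several weeks and then resolves. It posed no immediate threat to life, caused no stay over 24 hours, prolonged no existing stay, and needed no intervention to prevent permanent harm.

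| Criterion | In Protocol 5.1 list? | In SAP definition? | Met by the test event? |
|---|---|---|---|
| Death | Yes | Yes | No |
| Life-threatening | Yes | Yes | No |
| Hospitalization over 24 hours, or prolongation | Yes | Yes | No |
| Permanent impairment or damage | Yes | Yes | No |
| Intervention to avert permanent impairment or damage | Yes | Yes | No |
| Disability/incapacity, as Protocol 5.1 defines it | No | No | Yes |

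**2. Is the definition attached to anything?** The neighbouring definition of a life-threatening event explains a listed criterion. The disability/incapacity definition explains none, and the supplied text does not use the term elsewhere.

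**3. Does the important-medical-event clause close the gap?** It has two limbs. The intervention limb refers back to the listed outcomes, which do not include disability. The limb about jeopardizing the subject does not depend on the list, so it can reach the test event. But the clause is permissive, so two sites could classify the same event differently. The SAP definition has no such clause.

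**4. What depends on the serious label?**

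- Protocol 5.4.2: the 15-day IND report covers reactions and suspected reactions that are both serious and unexpected.
- Protocol 5.4.1: complete information within 5 working days and collection of source documents are required for SAEs.
- SAP 8.5.3: the table of serious TEAEs by SOC and preferred term.

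**5. What does not depend on it?**

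- Protocol 5.4.1 sets the 3-working-day deadline as follows: "Any serious adverse event or unexpected adverse event that occurs during this investigation, whether or not related to the study medication, must be reported". An unexpected event is therefore covered even if non-serious. Only an expected, non-serious event escapes this deadline.
- Protocol 5.2 requires every AE to be recorded and followed until it resolves or stabilizes.
- Protocol 6.3.6 and SAP 7.5 give the DSMB tables or listings that include all reported AEs.
- SAP 8.5.3 tabulates TEAEs by SOC and preferred term and by maximum severity. Protocol 5.2.2 grades as severe an event that markedly limits routine activities despite symptomatic therapy, which fits the test event.

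**The case against.** The strongest reply is that this is a drafting slip with little practical effect. Much of it stands.

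- **Other criteria catch some of these events.** A reader might infer that every disabling, reversible event without a stay over 24 hours goes uncounted as serious. The documents do not support that. Such an event qualifies if it threatened life, prolonged an existing stay, or needed intervention to avert permanent harm, and an investigator may also invoke the important-medical-event clause. The gap concerns events whose sole serious feature is significant, non-permanent disability.
- **Prompt reporting mostly survives.** A reader might infer that the sponsor would not hear within 3 working days. That is wrong for unexpected events. In the phase II study summarized in Protocol 1.4, the only related events were Grade 1 injection site reactions, so a lasting loss of walking would probably be unexpected. The Investigator Brochure, which decides this, is not among the documents.
- **The DSMB is not kept from the event.** A reader might infer that the DSMB would miss it. Both documents say that it reviews all reported AEs, and neither says that it relies on the serious TEAE table.
- **The working forms are unseen.** Protocol 5.4.1 has sites choose criteria on the SAE form and in the EDC. Neither is supplied, and they may already offer disability as an option.

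These points narrow the consequence but do not remove the inconsistency. Protocol 5.1 defines a category of harm that its own list does not use, and the SAP's definition is narrower still because it also lacks the discretionary clause.

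**Conclusion.** The point holds as an internal inconsistency: the text is wrong as written. An event whose only serious feature is significant but non-permanent disability meets no listed criterion in either document, and it becomes serious only through a discretionary clause that the SAP lacks. If such an event is recorded as non-serious, the protocol's wording leaves it outside the 15-day IND report and the SAE-specific duties, and it is missing from the serious TEAE table. It still appears as an AE.

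No number of affected events can be given. A reader might scale a percentage to the 318 planned VM202 subjects, but the documents give no rate to which that could be applied. The efficacy analyses are not touched.

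The conclusion assumes that sites classify by the written definition, since the SAE form and EDC options cannot be seen.

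**What to change.** Reconcile Protocol 5.1 with the SAP's Serious AE definition:

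1. Add disability/incapacity to both lists as a criterion, with the meaning that Protocol 5.1 already gives it.
2. Carry the important-medical-event clause into the SAP so that the two definitions match.
3. Check the SAE form and the EDC criteria, and add the option if it is missing. Protocol 5.2 records seriousness as a yes/no item and the SAP describes no re-derivation of it, so editing the SAP alone may change no table.
4. Have AEs already recorded re-checked for seriousness by reviewers blinded to treatment, before database lock. A re-check made with knowledge of assignment could bias the serious TEAE comparison.

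The cost is a written protocol amendment, with IRB approval before implementation where subject safety is affected (Protocol section 13), a SAP revision, possibly a form and EDC update, and one blinded review. A few AEs may be reclassified as serious.
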